#### **Data scopes for safety analyses for the pantoprazole/placebo randomization**

Analyses of safety outcomes for the pantoprazole randomization will be based on the safety analysis set related to the pantoprazole randomization. Subjects will be kept in the study group to which they were randomized. The outcome events will include:

- All outcome events observed from randomization until 2 days following permanent discontinuation of the pantoprazole study drug (“treatment emergent outcomes” analysis)
- All outcome events observed from randomization during the entire follow-up and wash-out periods up until the end of the trial

Corresponding censoring rules are described in Section 4.5.3.

### **4.5.3 Censoring Rules for Time-to-Event Variables**

For any time-to-event variable in this study, the following censoring rules will be applied:

#### **Censoring rules for analyses related to the rivaroxaban/aspirin randomization according to the intention-to-treat principle**

- For analyses according to the intention-to-treat principle which are related to the rivaroxaban/aspirin randomization and performed after the DSMB recommendation, randomized subjects without documentation of an evaluable event will be censored at

- the minimum (earliest) of the global rivaroxaban/aspirin outcomes cut-off date and the subject's last contact date during the rivaroxaban/aspirin portion of the study.

This censoring rule will be applied to all analyses according to the intention-to-treat principle. In the rare event that for a subject only survival status information can be retrieved at the end of the study rivaroxaban/aspirin portion of the trial but no information on other outcomes, the last study rivaroxaban/aspirin follow-up contact where survival status information was obtained will still be used to determine the censoring date for the subject and if there were no known events up to then the subject will be considered as event-free.

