telephone contact, unwillingness to have any contact with study personnel, or unwillingness to allow contact with a third party (e.g., family member, doctor). Every effort will be made to continue to follow the subject. Additionally, survival status and outcome information must be determined for all subjects at the end of the study. The expectation is that only very few subjects will have incomplete follow-up (in any form) within this trial.

A subject will be declared to have incomplete follow-up or to be lost to follow-up (i.e., to be completely non-compliant to follow-up) if, despite of all possible efforts, all investigators, dedicated site staff, the National Leader's Office and/or PPD Project Office (as applicable and as local regulations allow) are not able to contact the subject or to retrieve information about the subject from^32 a third party (e.g., family member, doctor). Every possible effort will be made to contact the subject or a third party and to determine the endpoint and survival status and reason for discontinuation as local law permits. If it is documented in the database that the subject is alive at the global rivaroxaban/aspirin outcomes cut-off date / at the end of the study, the subject will not be classified as lost to follow-up, but as alive.

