If a subject who is unable to attend his/her Final Follow-up Visit within the acceptable common trial close-out time-window, has a trial-related contact after the common trial close-out date, the observation period up until the common trial close-out date (inclusive) will be considered in the analysis.

For each subject, the following individual analysis dates will be derived:

- **Randomization date:**  
The date of randomization to antithrombotic treatment of the subject.
- **Date of the Final rivaroxaban/aspirin Follow-up Visit:**  
The date of the Final rivaroxaban/aspirin Follow-up Visit for the individual subject.  
If subjects do not have a Final rivaroxaban/aspirin Follow-up Visit, the date will be missing.
- **Final (pantoprazole/placebo) Follow-Up Visit date:**  
The date of the Final (pantoprazole/placebo) Follow-Up Visit for the individual subject.  
Beginning with the announcement of trial close-out, all subjects ongoing in the pantoprazole/placebo portion of the study are to return to the clinic for their Final Follow-Up Visit within the pre-specified common trial close-out window (see Section 3 for the schedule of evaluations at the Follow-Up Visit). If subjects do not have a Final Follow-Up Visit, the date will be missing.
- **Rivaroxaban/aspirin Washout Telephone Visit date:**  
The date of the rivaroxaban/aspirin Washout Telephone Visit for the individual subject. To be performed about 30 days after the Final rivaroxaban/aspirin Follow-up Visit.

- End of pantoprazole/placebo Washout (Telephone) Visit date:  
The date of the End of pantoprazole/placebo Washout Visit for the individual subject.  
To be performed about 30 days after the Final pantoprazole/placebo Follow-up Visit.  
If subjects do not have an End of pantoprazole/placebo Washout Visit, the date will be missing.
- Last contact date during rivaroxaban/aspirin portion of the study:  
The date of the last documented contact with the subject or a third party up until the maximum (later) of the subject's {date of the Final rivaroxaban/aspirin Follow-up Visit, end of rivaroxaban/aspirin Washout date}. For subjects who died after randomization but before their scheduled end of rivaroxaban/aspirin Washout date, the date of the last rivaroxaban/aspirin related contact is set to the death date.
- Date of the last follow-up contact:  
The date of the last known documented contact with the subject or a third party (including data on subject survival status)

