### **Censoring rules for analyses related to the pantoprazole/placebo randomization according to the intention-to-treat principle**

- For analyses according to the intention-to-treat principle, randomized subjects without documentation of an outcome event will be censored at
  - the subject's Final Follow-Up Visit if the subject attends the Final Follow-Up Visit before the common trial close-out date.
  - the subject's date of last follow-up contact up to the common trial close-out date (inclusive) if (a) the subject does not attend his/her Final Follow-Up Visit before the common trial close-out date and (b) the subject's date of last trial contact is not after the common trial close-out date.
  - the common trial close-out date if (a) the subject does not attend his/her Final Follow-Up Visit before the common trial close-out date and (b) the subject's date of last trial contact is after the common trial close-out date.

This censoring rule will be applied to all analyses related to the pantoprazole/placebo randomization performed after common trial close-out according to the intention-to-treat principle. In the rare event that for a subject only survival status information can be retrieved at the end of the study but no information on other outcomes, the last follow-up / trial contact where survival status information was obtained will still be used to determine the censoring date for the subject and if there were no known events up to then the subject will be considered as event-free.

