### 10.4.1 Definitions

In the context of missing data sensitivity analyses for the primary efficacy analysis we define, using the terms described in [Table 10-2](#),

---

 Text added as per modification 5 in integrated SAP, Version 4.1.

- a subject with unobserved rivaroxaban/aspirin follow-up time, as a rivaroxaban/aspirin follow-up non-completer for whom no unrefuted primary efficacy outcome event was documented and who is alive at the time of censoring,
- a subject’s observed rivaroxaban/aspirin follow-up time, as the time used in the primary efficacy outcome analysis (time under risk),
- a subject’s unobserved rivaroxaban/aspirin follow-up time, as the time from censoring to the global rivaroxaban/aspirin outcomes cut-off date for subjects with unobserved rivaroxaban/aspirin follow-up time and zero for subjects with no unobserved rivaroxaban/aspirin follow-up time.

With regard to the extent of “missing data”, we define

- the fraction of subjects with unobserved rivaroxaban/aspirin follow-up time, as the number of subjects with unobserved rivaroxaban/aspirin follow-up time divided by the number of subjects in the ITT population
- the fraction of missing rivaroxaban/aspirin follow-up subject-years, as the sum of the subjects’ unobserved rivaroxaban/aspirin follow-up time divided by the sum of the subjects’ observed and unobserved rivaroxaban/aspirin follow-up time

These definitions rely on the division of the ITT study population into rivaroxaban/aspirin follow-up completers and rivaroxaban/aspirin follow-up non-completers, see [Table 10-2](#).

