**Table 10-2. Definition of sensitivity analysis subject characteristics**

Subgroups	Definition
Rivaroxaban/aspirin follow-up non-completer	Subjects alive for whom 
 
• the last contact date during rivaroxaban/aspirin portion of the study is before the global rivaroxaban/aspirin outcomes cut-off date.
 

Rivaroxaban/aspirin follow-up completer	Subjects for whom 
 
• the last contact date during rivaroxaban/aspirin portion of the study is at or after the global rivaroxaban/aspirin outcomes cut-off date
 
• subject died
 

Rivaroxaban/aspirin study treatment non-completer	Subjects 
 
• who are rivaroxaban/aspirin follow-up non-completers and/or
 
• whose date of last rivaroxaban/rivaroxaban placebo or date of last aspirin/aspirin placebo study treatment is before the global rivaroxaban/aspirin outcomes cut-off date or before the subject’s death date (whatever comes first)
 

Rivaroxaban/aspirin study treatment completer	Subjects 
 
• who are rivaroxaban/aspirin follow-up completers and
 
• whose date of last rivaroxaban/rivaroxaban placebo and date of last aspirin/aspirin placebo study treatment is at or after the global rivaroxaban/aspirin outcomes cut-off date or identical to the death date
 

Note: the follow-up definitions from [Table 10-2](#) do not depend on

- premature discontinuation of study medication,

- the experience of an unrefuted primary efficacy outcome (rivaroxaban/aspirin follow-up non-completers may have experienced an unrefuted primary efficacy outcome event before premature discontinuation of their rivaroxaban/aspirin follow-up. However, only rivaroxaban/aspirin follow-up non-completers for whom no unrefuted primary efficacy outcome event is documented might impact the primary analysis due to missing outcome information.) and/or
- the reasons for being a rivaroxaban/aspirin follow-up non-completer, for example “complete withdrawal of informed consent”, “lost to follow-up”, or “other”.

Subjects who died are considered rivaroxaban/aspirin follow-up completers and having no missing outcome information, because subjects who experienced a terminal event cannot be followed-up.

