**6. Definitions**

Pantoprazole ITT analysis set	The pantoprazole ITT analysis set comprises all subjects that have been randomized to pantoprazole 40mg or pantoprazole placebo.
Final pantoprazole/placebo Follow-up Visit	Final visit at the end of the pantoprazole/placebo follow-up of the COMPASS trial
Pantoprazole/placebo Washout Visit	For subjects who participate in COMPASS in countries that have not yet approved the protocol amendment no. 11 forming integrated protocol version 4.0, an End of Washout Telephone Visit (Washout Visit) is envisaged 30 days post Final pantoprazole/placebo Follow-up Visit.
Last rivaroxaban/aspirin Follow-up Date	
If consent was not withdrawn:
 
Last rivaroxaban/aspirin Follow-up Date
 
= first of
 
 
• date of death (if applicable)
 
• date of completed Final rivaroxaban/aspirin Follow-up visit (if applicable)
 
• max (dates of visits completed, event dates).
 
 
If consent was withdrawn:
 
Last rivaroxaban/aspirin Follow-up Date
 
= first of
 
 
• max (date of death, date of withdrawal, date of confirmed alive)
 
• date of completed Final rivaroxaban/aspirin Follow-up visit (if applicable).
 

Last pantoprazole/placebo Follow-up Date	
If consent was not withdrawn:
 
Last pantoprazole/placebo Follow-up Date
 
= first of
 
 
• date of death (if applicable)
 
• date of completed Final pantoprazole/placebo Follow-up visit (if applicable)
 

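### Follow-up known only as "alive" counts as observed and event-free, so for subjects known alive at or after the cut-off the Appendix 10.4 missing-data analysis leaves that time out

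*SAP*

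**What the plan says.** **Censoring.** In Section 4.5.3 of the integrated SAP (version 4.1), the intention-to-treat rule for the rivaroxaban/aspirin randomization covers subjects with survival status but no information on other outcomes. For them "the last study rivaroxaban/aspirin follow-up contact where survival status information was obtained will still be used to determine the censoring date", and "if there were no known events up to then the subject will be considered as event-free". The rule for the pantoprazole randomization is parallel: "the last follow-up / trial contact where survival status information was obtained will still be used to determine the censoring date".

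**Last contact.** Section 4.5.1 defines the last contact in the rivaroxaban/aspirin portion as "The date of the last documented contact with the subject or a third party up until the maximum (later") of the final visit and the end of washout. Outcome ascertainment at that contact is not required.

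**Loss to follow-up.** Under Section 4.2, if a subject is documented alive at the cut-off or at study end, "the subject will not be classified as lost to follow-up, but as alive".

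**Missing-data analysis.** Table 10-2 makes a subject a follow-up completer if "the last contact date during rivaroxaban/aspirin portion of the study is at or after the global rivaroxaban/aspirin outcomes cut-off date", or if the subject died. Section 10.4.1 sets unobserved time to "zero for subjects with no unobserved rivaroxaban/aspirin follow-up time". Step 2 of Section 10.4.3 imputes only subjects with missing follow-up time under that definition.

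**PPI close-out SAP.** Section 6 defines the last follow-up date after consent withdrawal as the first of "max (date of death, date of withdrawal, date of confirmed alive") and the completed final visit.

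**The concern.** A survival-status contact is full ascertainment for death and no ascertainment for non-fatal events. Carrying the subject as event-free to that contact adds person-time to the risk sets in which a non-fatal MI or stroke could not have been recorded. Event rates are then biased downward. The hazard ratio is biased only if such gaps differ between arms.

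The larger problem is in Appendix 10.4, which was written to measure and stress-test missing primary-outcome follow-up. Its definitions classify this kind of missingness as complete data. The reported fractions of missing subjects and missing subject-years, and the tipping-point factors F and G, would then describe only subjects with no contact at all up to the cut-off.

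**Working it through.** No figure in the plan is in dispute, so the check traces one type of subject through the definitions. The size is illustrated afterwards.

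**Trace.** Take a subject who stops giving outcome information at time *t*, with no event known, and is later confirmed alive.

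1. *Confirmed alive on or after 06 February 2017.* The last contact (Section 4.5.1) is the alive contact. Section 4.5.3 censors at the cut-off date, event-free. Table 10-2 makes the subject a completer. Section 10.4.1 gives zero unobserved time. Section 10.4.3 imputes nothing for *t* to the cut-off.
2. *Confirmed alive before 06 February 2017.* The subject is a non-completer. Time from the alive contact to the cut-off is unobserved and imputed. The gap from *t* to the alive contact still counts as observed and event-free.
3. The repeat described at the end of Section 10.4.3 fits the imputation model to all randomized subjects. It changes who informs the model, not who is imputed.

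Case 1 should be the usual one. The rule concerns status retrieved at the end of the rivaroxaban/aspirin portion, and the close-out window runs from the end of February to 15 May 2017, after the cut-off.

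**Internal tension.** Appendix 10.4 names complete withdrawal of consent as a source of unobserved time. Section 3 says withdrawal does not end permission to collect vital status, so a withdrawn subject later found alive becomes a completer. Section 4.5.2 ends the data scope at complete refusal to give further information, yet Section 4.5.3 extends time at risk to the survival-status contact.

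**GI outcome.** The GI analysis in the PPI close-out SAP uses that document's own last follow-up date. For subjects who did not withdraw, it rests on death, the completed final visit, or the latest completed visit or event, with no confirmed-alive term. For withdrawn subjects it passes the withdrawal date when a later confirmed-alive date exists.

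**Illustrative size.** From the SAP: 27,400 subjects; about 1,100 events at the first interim analysis; planned events of 826 in control and 687 per rivaroxaban arm out of 2,200; overall incidence 2.9% per year. Assumed: 1–3% of subjects with vital status only, for one year, and non-fatal MI or stroke at 1.5–2% per year.

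- Person-time: 27,400 × 0.01 × 1 = 274 to 27,400 × 0.03 × 1 = 822 person-years.
- Unseen events: 274 × 0.015 = 4.1 to 822 × 0.02 = 16.4, so about 4–16.
- Share of all person-time: 1,100 / 0.029 = 37,931 person-years; 274 / 37,931 = 0.7% and 822 / 37,931 = 2.2%. In case 1 the plan's missing fraction counts this as 0.
- Events per arm at 1,100: control 1,100 × 826 / 2,200 = 413; each rivaroxaban arm 1,100 × 687 / 2,200 = 343.5.

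For the hazard ratio, let two thirds of the 4–16 unseen events fall in the two compared arms (2.67 to 10.67), split 2:1. The observed HR is then the true HR times (1 − share missed on rivaroxaban) / (1 − share missed on control).

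| Double share in | Unseen events, total | Missed, rivaroxaban | Missed, control | Change in HR |
|---|---|---|---|---|
| Control | 4 | 0.89/343.5 = 0.26% | 1.78/413 = 0.43% | +0.2% |
| Control | 16 | 3.56/343.5 = 1.04% | 7.11/413 = 1.72% | +0.7% |
| Rivaroxaban | 4 | 1.78/343.5 = 0.52% | 0.89/413 = 0.22% | −0.3% |
| Rivaroxaban | 16 | 7.11/343.5 = 2.07% | 3.56/413 = 0.86% | −1.2% |

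If equal shares of events are missed in both arms, the factor is 1.

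**The case against.** The rule is stated openly and described as rare. Sections 3 and 4.2 require outcome information as well as survival status for all subjects, allow third-party retrieval of both, and expect very few subjects with incomplete follow-up. A late contact should therefore not be presumed to be vital-status-only. This stands, and it limits the likely size. It does not repair the definitions, which still count the gap as observed when it occurs.

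A second objection concerns the remedy. Censoring survivors at the last outcome contact, while still counting cardiovascular deaths found by the same survival search, makes follow-up depend on outcome and pushes composite rates upward. For cardiovascular and CHD death, confirmation of being alive is complete information. This also stands. It argues against replacing the primary censoring rule, and for a sensitivity analysis.

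A reader might infer that every vital-status-only subject is a completer. Case 2 shows otherwise. A reader might also infer that the PPI close-out SAP extends GI follow-up for everyone who withdrew consent. It does so only where a confirmed-alive date falls after withdrawal. Nor does the Appendix 10.4 criticism reach GI outcomes, because that appendix covers only the primary efficacy outcome.

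**Conclusion.** The point holds in limited form. Subjects with survival status only are treated as free of non-fatal events up to that contact. If they are known alive on or after 06 February 2017, the whole gap is absent from the missing-data fractions, the imputation and the tipping-point analysis. If the contact is earlier, only the gap before it is absent. All-cause mortality is unaffected.

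The size rests wholly on assumed frequencies. About 4–16 events and 0.2–1.2% on the HR under a 2:1 imbalance are small beside the planned 20% relative risk reduction, and with balanced gaps the HR is essentially unchanged. A reader might conclude that the primary result is unreliable; neither the documents nor these figures support that. What is wrong is that Appendix 10.4 does not test part of the missingness it sets out to test.

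**What to change.** 1. Derive a last-outcome-ascertainment date for each subject: the latest visit, call or third-party contact at which outcomes were asked about.
2. In Table 10-2 and Section 10.4.1, define completion and unobserved time by that date. Vital-status-only gaps then count as missing. Where the subject is known to have been alive throughout, impute only non-fatal MI and stroke in the gap.
3. Report the number of vital-status-only subjects and their person-time by arm.
4. Add a sensitivity analysis that censors the non-fatal components of the primary outcome at that date, and one for the GI outcome that censors at withdrawal or last outcome contact. State in advance how cardiovascular deaths found after that date enter the composite.
5. Keep the vital-status date for all-cause, cardiovascular and CHD death.

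The cost is one more derived date, some SAP wording, and a somewhat higher reported missing-data fraction.

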### **Censoring rules for analyses related to the pantoprazole/placebo randomization according to the intention-to-treat principle**

- For analyses according to the intention-to-treat principle, randomized subjects without documentation of an outcome event will be censored at
  - the subject's Final Follow-Up Visit if the subject attends the Final Follow-Up Visit before the common trial close-out date.
  - the subject's date of last follow-up contact up to the common trial close-out date (inclusive) if (a) the subject does not attend his/her Final Follow-Up Visit before the common trial close-out date and (b) the subject's date of last trial contact is not after the common trial close-out date.
  - the common trial close-out date if (a) the subject does not attend his/her Final Follow-Up Visit before the common trial close-out date and (b) the subject's date of last trial contact is after the common trial close-out date.

This censoring rule will be applied to all analyses related to the pantoprazole/placebo randomization performed after common trial close-out according to the intention-to-treat principle. In the rare event that for a subject only survival status information can be retrieved at the end of the study but no information on other outcomes, the last follow-up / trial contact where survival status information was obtained will still be used to determine the censoring date for the subject and if there were no known events up to then the subject will be considered as event-free.

### **Censoring rules for secondary safety analyses related to the rivaroxaban/aspirin randomization**

- For secondary safety analyses based on the safety analysis set and the ITT data scope, all randomized subjects with at least one dose of either randomized study medication and without documentation of an outcome event within the ITT data scope will be censored as stated above for study rivaroxaban/aspirin analyses according to the ITT principle.
- For "treatment-emergent" secondary safety analyses, all randomized subjects with at least one dose of study medication and without documentation of an outcome event within the

 Text modified as per modification 1 in integrated SAP, Version 3.0.

 Text modified as per modification 1 in integrated SAP, Version 3.0.

 Text modified as per modification 1 in integrated SAP, Version 3.0.

“treatment-emergent” data scope will be censored at the date of last double-blind dose of antithrombotic study treatment + 2 days.

Note that if a subject stops treatment at the Final rivaroxaban/aspirin Follow-up Visit and experiences an event up to 2 days thereafter, the event will be counted in this analysis but not in the primary analysis using the ITT data scope.

- For secondary safety analyses based on the safety analysis set and the “plus 30 days safety” data scope, all randomized subjects with at least one dose of study medication and without documentation of an outcome event within the “plus 30 days safety” data scope will be censored at the date of last double-blind dose of antithrombotic study treatment + 30 days.

Note that if a subject stops treatment at the Final rivaroxaban/aspirin Follow-up Visit and experiences an event up to 30 days thereafter, the event will be counted in this analysis but not in the primary analysis using the ITT data scope.

- For secondary safety analyses based on the safety analysis set and the “Study rivaroxaban/aspirin Follow up + Wash out” data scope, all randomized subjects with at least one dose of study medication and without documentation of an outcome event will be censored at the subject’s last contact date during the rivaroxaban/aspirin portion of the study.

